9. RESPONSIBILITIES

9.1. Investigator Responsibilities

9.1.1. Good Clinical Practice

The investigator will ensure that this study is conducted in accordance with the principles of the Declaration of Helsinki (as amended in Edinburgh, Tokyo, Venice, Hong Kong, and South Africa), International Conference on Harmonisation (ICH) guidelines, or with the laws and regulations of the country in which the research is conducted, whichever affords the greater protection to the study subject. These standards are consistent with the European Union Clinical Trials Directive 2001/20/EC and Good Clinical Practice Directive 2005/28/EC.

The investigator will ensure adherence to the basic principles of Good Clinical Practice, as outlined in 21 CFR 312, subpart D, "Responsibilities of Sponsors and Investigators," 21 CFR, part 50, 1998, and 21 CFR, part 56, 1998.

The investigator and all applicable sub-investigators will comply with 21 CFR, Part 54, 1998, providing documentation of their financial interest or arrangements with Gilead, or proprietary interests in the investigational drug under study. This documentation must be provided prior to the investigator's (and any sub-investigator's) participation in the study. The investigator and sub-investigator agree to notify Gilead of any change in reportable interests during the study and for 1 year following completion of the study. Study completion is defined as the date when the last subject completes the protocol-defined activities.

9.1.2. Institutional Review Board (IRB)/Independent Ethics Committee (IEC) Review and Approval

The investigator (or sponsor as appropriate according to local regulations) will submit this protocol, informed consent form, and any accompanying material to be provided to the subject (such as advertisements, subject information sheets, or descriptions of the study used to obtain informed consent) to an IRB/EC. The investigator will not begin any study subject activities until approval from the IRB/EC has been documented and provided as a letter to the investigator.

Before implementation, the investigator will submit to and receive documented approval from the IRB/EC any modifications made to the protocol or any accompanying material to be provided to the subject after initial IRB/EC approval, with the exception of those necessary to reduce immediate risk to study subjects.

9.1.3. Informed Consent

The investigator is responsible for obtaining written informed consent from each individual participating in this study after adequate explanation of the aims, methods, objectives, and potential hazards of the study and before undertaking any study-related procedures. The investigator must use the most current IRB- or IEC-approved consent form for documenting

written informed consent. Each informed consent will be appropriately signed and dated by the subject and the person conducting the consent discussion, and also by an impartial witness if required by IRB, IEC, or local requirements. The consent form will inform subjects about pharmacogenomic testing and sample retention, and their right to receive clinically relevant pharmacogenomic analysis results.

9.1.4. Confidentiality

The investigator must assure that subjects' anonymity will be strictly maintained and that their identities are protected from unauthorized parties. Only subject initials, date of birth, another unique identifier (as allowed by local law) and an identification code will be recorded on any form or biological sample submitted to the Sponsor, IRB/IEC, or laboratory. Laboratory specimens must be labeled in such a way as to protect subject identity while allowing the results to be recorded to the proper subject. Refer to specific laboratory instructions. NOTE: The investigator must keep a screening log showing codes, names, and addresses for all subjects screened and for all subjects enrolled in the trial. Subject data will be processed in accordance with all applicable regulations.

The investigator agrees that all information received from Gilead, including but not limited to the investigator brochure, this protocol, CRF/eCRF, the IMP, and any other study information, remain the sole and exclusive property of Gilead during the conduct of the study and thereafter. This information is not to be disclosed to any third party (except employees or agents directly involved in the conduct of the study or as required by law) without prior written consent from Gilead. The investigator further agrees to take all reasonable precautions to prevent the disclosure by any employee or agent of the study site to any third party or otherwise into the public domain.

9.1.5. Study Files and Retention of Records

The investigator must maintain adequate and accurate records to enable the conduct of the study to be fully documented and the study data to be subsequently verified. These documents should be classified into at least the following two categories: (1) investigator's study file, and (2) subject clinical source documents.

The investigator's study file will contain the protocol/amendments, CRF and query forms, IRB/IEC and governmental approval with correspondence, informed consent, drug records, staff curriculum vitae and authorization forms, and other appropriate documents and correspondence.

The required source data should include sequential notes containing at least the following information for each subject:

- Subject identification (name, date of birth, gender);
- Documentation that subject meets eligibility criteria, ie., history, physical examination, and confirmation of diagnosis (to support inclusion and exclusion criteria);

- Documentation of the reason(s) a consented subject is not enrolled
- Participation in study (including study number);
- Study discussed and date of informed consent;
- Dates of all visits;
- Documentation that protocol specific procedures were performed;
- Results of efficacy parameters, as required by the protocol;
- Start and end date (including dose regimen) of study drug including dates of dispensing and return;
- Record of all adverse events and other safety parameters (start and end date, and including causality and severity);
- Concomitant medication (including start and end date, dose if relevant; dose changes);
- Date of study completion and reason for early discontinuation, if it occurs.

All clinical study documents must be retained by the investigator until at least 2 years or according to local laws, whichever is longer, after the last approval of a marketing application in an ICH region (ie, United States, Europe, or Japan) and until there are no pending or planned marketing applications in an ICH region; or, if no application is filed or if the application is not approved for such indication, until 2 years after the investigation is discontinued and regulatory authorities have been notified. Investigators may be required to retain documents longer if specified by regulatory requirements, by local regulations, or by an agreement with Gilead. The investigator must notify Gilead before destroying any clinical study records.

Should the investigator wish to assign the study records to another party or move them to another location, Gilead must be notified in advance.

If the investigator cannot provide for this archiving requirement at the study site for any or all of the documents, special arrangements must be made between the investigator and Gilead to store these records securely away from the site so that they can be returned sealed to the investigator in case of an inspection. When source documents are required for the continued care of the subject, appropriate copies should be made for storage away from the site.

9.1.6. Case Report Forms

For each subject consented, an eCRF will be completed by an authorized study staff member whose training for this function is documented according to study procedures. eCRF should be completed on the day of the subject visit to enable the sponsor to perform central monitoring of safety data. The Eligibility Criteria eCRF should be completed only after all data related to

eligibility have been received. Subsequent to data entry, a study monitor will perform source data verification within the EDC system. Original entries as well as any changes to data fields will be stored in the audit trail of the system. Prior to database lock (or any interim time points as described in the clinical data management plan), the investigator will use his/her log in credentials to confirm that the forms have been reviewed, and that the entries accurately reflect the information in the source documents. The eCRF capture the data required per the protocol schedule of events and procedures. System-generated or manual queries will be issued to the investigative site staff as data discrepancies are identified by the monitor or internal Gilead staff, who routinely review the data for completeness, correctness, and consistency. The site coordinator is responsible for responding to the queries in a timely manner, within the system, either by confirming the data as correct or updating the original entry, and providing the reason for the update (eg data entry error). At the conclusion of the trial, Gilead will provide the site with a read-only archive copy of the data entered by that site. This archive must be stored in accordance with the records retention requirements outlined in Section 9.1.5.

9.1.7. Investigational Medicinal Product Accountability and Return

Gilead recommends that used and unused IMP supplies be returned to the shipping facility from which it came for eventual destruction. The study monitor will provide instructions for return. If return is not possible, the study monitor will evaluate each study center's IMP disposal procedures and provide appropriate instruction for destruction of unused IMP supplies. If the site has an appropriate standard operating procedure (SOP) for drug destruction as determined by Gilead QA, the site may destroy used (empty or partially empty) and unused IMP supplies in accordance with that site's approved SOP. A copy of the site's approved SOP will be obtained for central files.

If IMP is destroyed on site, the investigator must maintain accurate records for all IMP destroyed. Records must show the identification and quantity of each unit destroyed, the method of destruction, and the person who disposed of the IMP. Upon study completion, copies of the IMP accountability records must be filed at the site. Another copy will be returned to Gilead.

The study monitor will review IMP supplies and associated records at periodic intervals.

9.1.8. Inspections

The investigator will make available all source documents and other records for this trial to Gilead's appointed study monitors, or to regulatory authority or health authority inspectors.

9.1.9. Protocol Compliance

The investigator is responsible for ensuring the study is conducted in accordance with the procedures and evaluations described in this protocol.

9.2. Sponsor Responsibilities

9.2.1. Protocol Modifications

Protocol modifications, except those intended to reduce immediate risk to study subjects, may be made only by Gilead. The investigator must submit all protocol modifications to the IRB [or] IEC in accordance with local requirements and receive documented IRB [or] IEC approval before modifications can be implemented.

9.2.2. Study Report and Publications

A clinical study report (CSR) will be prepared and provided to the regulatory agency. Gilead will ensure that the report meets the standards set out in the ICH Guideline for Structure and Content of Clinical Study Reports (ICH E3). Note that an abbreviated report may be prepared in certain cases.

Investigators in this study may communicate, orally present, or publish in scientific journals or other scholarly media only after the following conditions have been met:

The results of the study in their entirety have been publicly disclosed by or with the consent of Gilead in an abstract, manuscript, or presentation form or the study has been completed at all study sites for at least 2 years

The investigator will submit to Gilead any proposed publication or presentation along with the respective scientific journal or presentation forum at least 30 days before submission of the publication or presentation.

No such communication, presentation, or publication will include Gilead's confidential information

The investigator will comply with Gilead's request to delete references to its confidential information (other than the study results) in any paper or presentation and agrees to withhold publication or presentation for an additional 60 days in order to obtain patent protection if deemed necessary.

9.3. Joint Investigator/Sponsor Responsibilities

9.3.1. Payment Reporting

Investigators and their study staff may be asked to provide services performed under this protocol, eg attendance at Investigator's Meetings. If required under the applicable statutory and regulatory requirements, Gilead will capture and disclose to Federal and State agencies any expenses paid or reimbursed for such services, including any clinical trial payments, meal, travel expenses or reimbursements, consulting fees, and any other transfer of value.

9.3.2. Access to Information for Monitoring

In accordance with regulations and guidelines, the study monitor must have direct access to the investigator's source documentation in order to verify the accuracy of the data recorded in the CRF/eCRF.

The monitor is responsible for routine review of the CRF/eCRF at regular intervals throughout the study to verify adherence to the protocol and the completeness, consistency, and accuracy of the data being entered on them. The monitor should have access to any subject records needed to verify the entries on the CRF/eCRF. The investigator agrees to cooperate with the monitor to ensure that any problems detected through any type of monitoring (central, on site) are resolved.

9.3.3. Access to Information for Auditing or Inspections

Representatives of regulatory authorities or of Gilead may conduct inspections or audits of the clinical study. If the investigator is notified of an inspection by a regulatory authority the investigator agrees to notify the Gilead medical monitor immediately. The investigator agrees to provide to representatives of a regulatory agency or Gilead access to records, facilities, and personnel for the effective conduct of any inspection or audit.

9.3.4. Study Discontinuation

Both the sponsor and the investigator reserve the right to terminate the study at any time. Should this be necessary, both parties will arrange discontinuation procedures and notify the appropriate regulatory authority(ies), IRBs, and IECs. In terminating the study, Gilead and the investigator will assure that adequate consideration is given to the protection of the subjects' interests.

Appendix 2. Study Visit Schedule

Study Visits: Blinded Period									
Week ^a	Screening ^b	Day 1	Week 1	Week 4	Week 8	Week 12 ^q	ESDD ^d	Unscheduled Visit ^t	30 Day Follow-up
Window in Days	-35 days	0	±3	±3	±3	±3	±3		±5
Written Informed Consent ^c	X								
Confirmation of RA diagnosis	X								
Medical/Surgical History	X								
Complete Physical Exam	X					X	X		
Targeted Physical Exam ^e		X	X	X	X	X		X	X
Concomitant Medications	X	X	X	X	X	X	X	X	
Vital Signs & Weight ^f	X	X	X	X	X	X	X	X	X
Height	X								
Adverse Events	X	X	X	X	X	X	X	X	X
12 lead ECG ^s	X					X	X ^s		
High sensitivity C-Reactive Protein (hsCRP)	X	X	X	X	X	X	X	X	X
Serum β-HCG Pregnancy Test ^g	X					X	X		X
Urine Pregnancy test ^g		X		X	X			X	
Rheumatoid Factor and anti-CCP antibodies	X								
QuantiFERON-Gold (QFT) blood test	X								
Chest X-Ray ^h	X								
HIV Serology	X								

Study Visits: Blinded Period									
Week ^a	Screening ^b	Day 1	Week 1	Week 4	Week 8	Week 12 ^q	ESDD ^d	Unscheduled Visit ^t	30 Day Follow-up
Window in Days	-35 days	0	±3	±3	±3	±3	±3		±5
Hepatitis BsAg and Core Ab (if positive core Ab, then reflex Hep B DNA) ⁱ Hepatitis C Ab (if positive, then reflex HCV RNA) ^j	X					X			
Estimated Glomerular Filtration Rate (based on MDRD study equation) performed by central lab	X					X	X		X
Erythrocyte Sedimentation Rate (ESR) Local Lab		X	X	X	X	X	X	X	
Hematology ^j	X	X	X	X		X	X	X	X
Chemistry ^k	X	X	X	X		X	X	X	X
Urinalysis	X	X	X	X	X	X	X	X	X
66 swollen and 68 tender joint count assessment	X	X	X	X	X	X	X	X ^t	X
Thyroid Stimulating Hormone (TSH)	X								
Glycated Hemoglobin (HbA1c)	X								
CD19 Flow cytometry (patients who have taken rituximab or any B cell depleting agent)	X								
Disease Specific Questionnaire and Activity Scales	X	X	X	X	X	X	X	X ^t	X
Health Assessment Questionnaire Disability Index (HAQ-DI)		X	X	X	X	X	X		X

Study Visits: Blinded Period									
Week ^a	Screening ^b	Day 1	Week 1	Week 4	Week 8	Week 12 ^q	ESDD ^d	Unscheduled Visit ^t	30 Day Follow-up
Window in Days	-35 days	0	±3	±3	±3	±3	±3		±5
Short Form (36) Health Survey (SF-36)		X	X	X	X	X	X		X
Pharmacokinetics (PK) ^l			X	X	X	X	X		
Optional PK Sub-Study (Day 4 or Day 6) ^m		X							
GS-5745 ADA collection ⁿ		X		X	X	X			X
Biomarkers (blood samples)		X		X		X			
Optional genomic testing ^o		X							
Randomization		X							
Study Drug Administration ^p		X	X	X	X	X (for subjects continuing to OLE)			
Study Drug Dispensing ^r		X	X	X	X	X (for subjects continuing to OLE)			

a All visits scheduled relative to Day 1

b Evaluations are to be completed within 35 days prior to Day 1.

c Consent must be signed prior to any study evaluations

d Early Study Drug Discontinuation visit to occur within 72 hours of last dose of study drug, as much as possible

e Symptom-directed physical exam as needed

f Vital Signs include blood pressure, pulse, respirations, temperature

g Women of child-bearing potential only, as defined per protocol

h Chest x-ray should be performed at Screening, unless done in the previous 90 days, with films or results available at the site

i If HB Core Ab and/or HC Ab are positive during screening but their respective DNA or RNA PCR tests are negative, the PCR test should be repeated every 3 months

j Refer to [Appendix 12](#) for complete laboratory assessments

k Refer to [Appendix 12](#) for complete laboratory assessments

l Prior to dose at Week 1, 4, 8, and anytime at week 12 and ESDD (if applicable)

m Anytime on Day 4 (+/- 1) or Day 6 (+/- 1) after Day 1 dose (for subjects who consent to optional PK substudy only)

- n Prior to dose on Study Days 1, Week 4, 8, anytime on Week 12 , and 30 day follow-up
- o Collection of blood for DNA analysis will be optional for subjects and will be collected at Day 1 or at any other visit during the course of the study
- p Subjects will receive weekly SC injections of GS-5745. SC Study Drug Administration will occur at the study site on study Day 1, Week 1, Week 4, and Week 8. Subjects will remain at the study site for 30 minutes after the injection for observation on Day 1 and Week 1. The observation period may be extended as per judgment of the investigator. After receiving SC instruction at the study site during the first 2 drug SC injections, subjects judged capable will be allowed to self-administer weekly SC injections at home.in the blinded and OLE periods. Subjects not eligible or choosing not to participate in the OLE will come in for Week 12 visit assessments will not be administered study drug. Subjects that are eligible and choose to participate in the OLE will receive their first dose of study drug in the OLE of the study on Week 12 after completing all the requirements of Week 12 of the blinded period of the study.
- q Subjects not participating in the OLE will complete all week 12 assessments but will not receive an injection of study drug at the Week 12 visit. If subjects are eligible to participate in the OLE, then subjects complete all Week 12 assessments for the blinded period and then receive the first dose of the drug for OLE.
- r Study drug for 4 weekly doses will be dispensed at Weeks 1, 4 and 8
- s If not done in the prior 12 weeks. ECGs are to be performed supine
- t Per discretion of investigator

Study Visits: Open Label Extension														
Week	12	13	19	24	30	36	42	48	54	60	64	30 Day Follow Up	Unscheduled Visit ^k	ESDD
Window in Days	±3	±3	±5	±5	±5	±5	±5	±5	±5	±5	±5	±5		±3
Complete physical exam												X		
Targeted physical exam ^b		X	X	X	X	X	x	X	X	X	X	X	X	X
Vital signs and weight ^a		X	X	X	X	X	X	X	X	X	X	X	X	X
12 lead ECG											X		X ^k	
66 swollen and 68 tender joint count assessment				X		X		X		X	X	X	X ^k	X
Disease Specific Questionnaires and Activity Scales				X		X		X		X	X	X	X ^k	X
HAQ-DI				X		X		X		X	X	X	X ^k	X
SF-36				X		X		X		X	X	X	X ^k	X
Hematology ^c		X	X	X	X	X	X	X	X	X	X	X	X	X
Chemistry panel ^c		X	X	X	X	X	X	X	X	X	X	X	X ^k	X
Urinalysis		X	X	X	X	X	X	X	X	X	X	X		X
Erythrocyte Sedimentation Rate (ESR) Local lab			X	X	X	X	X	X	X	X	X	X		X
serum β-HCG Pregnancy Test ^d												X		X

Study Visits: Open Label Extension														
Week	12	13	19	24	30	36	42	48	54	60	64	30 Day Follow Up	Unscheduled Visit ^k	ESDD
Window in Days	±3	±3	±5	±5	±5	±5	±5	±5	±5	±5	±5	±5		±3
Urine Pregnancy test at study visits as marked – and every 4 weeks using kit at home (at weeks 16, 20, 28, 32, 40, 44, 52, and 56) ^d				X		X		X		X	X		X	
PK collection ^e				X							X			X
GS-5745 ADA collection ^f			X								X	X		
Biomarker collection	X			X		X		X		X				
C-Reactive Protein (hsCRP)		X	X	X	X	X	X	X	X	X	X	X	X	X
QuantiFERON-GOLD (QFT)									X					X
Chest x-ray (based on local TB screening guidelines)									X					
Estimated Glomerular Filtration Rate (based on MDRD study equation) performed at central lab				X		X		X		X				X

Study Visits: Open Label Extension														
Week	12	13	19	24	30	36	42	48	54	60	64	30 Day Follow Up	Unscheduled Visit ^k	ESDD
Window in Days	±3	±3	±5	±5	±5	±5	±5	±5	±5	±5	±5	±5		±3
Study Drug Dispensing ^g	X		X	X	X	X	X	X	X	X	no			
Study Drug Administration ^h														
Concomitant medications ⁱ	X	X	X	X	X	X	X	X	X	X	X	X	X	
Adverse Events ⁱ	X	X	X	X	X	X	X	X	X	X	X	X	X	
HBV DNA testing for subjects with positive Hep B serology every 3 months if positive HCV RNA testing for subjects with positive hep C serology every 3 mos if positive ^j				X		X		X		X				

a Vital Signs include blood pressure, pulse, respirations, temperature

b Symptom-directed physical exam as needed

c Refer to [Appendix 12](#) for complete laboratory assessments

d Women of child bearing potential only. Patients will be supplied with home urine pregnancy kits and instructed to test every 4 weeks. Site will follow-up with a phone call to obtain and record results (subject with positive test should immediately discontinue study drug and present to the site for a serum pregnancy test). Pregnancy form should be completed should a pregnancy occur,

[figure not shown]
e Prior to drug dose on (Week 24) and anytime on (Week 64)

f Prior to study dose on (Week 24) and any time on (week 64), the 30 day follow-up

g a 6 week supply of drug (6 doses)will be dispensed at these visits except for Week 12, 13 and week 64 when 1 dose will be dispensed. Site personnel will administer study drug at office visits when drug is dispensed

- h Patients receive SC injections once a week SC Study drug administration will occur at the study site for the first 2 doses in the OLE at Week 12 and Week 13. Subjects will remain at the study site for 30 minutes after the injection for observation at week 12 and week 13. The observation period may be extended as per judgment of the investigator. If subjects are judged capable, subjects may administer study drug at home for the remainder of the study. SC Study drug administration and anti-TNF administration must be separated in time by at least 24 hours in the blinded and OLE of the study. Subjects should record study drug administration in study drug diary
- i Con meds and adverse events will be recorded throughout the study. Patients will be questioned on con med and adverse events at in office visits
- j If HB Core Ab and/or HCV Ab are positive during screening, then their respective DNA or RNA PCR test should be repeated every 3 months
- k Per discretion of investigator

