 - a) Carcinoma in situ of the cervix that has been successfully treated
 - b) Adequately treated basal or squamous cell cancer that has been successfully treated

Study Procedures/
Frequency:

All subjects will have the following visits at the study site during the blinded period of the study: Screening, Day 1 (first dose of study drug) and Weeks 1, 4, 8 and 12. Subjects will receive the first two injections of study drug (Day 1 and Week 1) at the study site. After completion of the 12 week blinded period of the study, subjects will have the option to participate in the OLE in the same protocol. Subjects who do not participate in the OLE will complete Week 12 assessments and will not receive open label study drug. These subjects

will have a follow up visit 30 days after their last dose of study drug.

Subjects who are eligible will receive their first dose of OLE study drug at Week 12, after completing all the required assessments of the Week 12 visit. Additional OLE study visits will occur at Weeks 13, 19, 24, 30, 36, 42, 48, 54, 60, and 64, with a follow-up visit 30 days after the subject's last dose of study drug.

Screening Assessments

- Confirmation of RA diagnosis
- Medical/Surgical history
- Vital signs to include blood pressure, pulse, temperature and respiration
- Complete physical exam (CPE) height and weight
- 12 lead ECG
- Central laboratory tests including Rheumatoid Factor, anti-CCP, complete blood count, hematology, chemistry panel, urinalysis, urine drug screen, serum β -HCG (women of childbearing potential), QuantiFERON® TB-Gold In-Tube test, HIV, Hepatitis B and C testing (with reflex testing if positive for antibodies), CRP, Estimated Glomerular Filtration Rate (based on MDRD study equation), TSH and HbA1c. Flow cytometry for absolute CD19+ B-cell counts (subjects who have taken rituximab or any B cell depleting agent)
- A negative chest X-ray (views per local guidelines) for active lung disease at Screening; or a chest X-ray within 90 days of Screening if films and/or report are available for investigator review.
- 66 swollen and 68 tender joint counts
- Patient's and Physician's Global Assessment of Health
- Patient's Assessment of Pain

On-Treatment Assessments

- Concomitant medications
- Vital signs to include blood pressure, pulse, temperature, respiration, and weight
- CPE (Blinded period Week 12 and Week 64 only); targeted Physical exam (TPE) at all other visits
- 12-lead ECG (Week 12 blinded period and Week 64 only)

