In the OLE, study drug administration will occur weekly from Week 12 to Week 64. SC study drug administration will occur at the study site for the first 2 doses in the OLE at Weeks 12 and 13. Subjects will remain at the study site for at least 30 minutes after the first 2 injections of study drug for observation. This time may be extended per judgment of the investigator. (Subjects are to be scheduled for a 30-day follow-up visit after their last dose of study

drug.

Routine SC administration of the subject's own TNF inhibitor identified during Screening should continue throughout the study, as per the local label.

PK and Biomarker Sampling:

PK Blood Draws: PK blood draws will be done prior to dosing at Weeks 1, 4, and 8, anytime at Week 12 and at ESDD (if applicable), prior to dosing at Week 24 and anytime at Week 64 of the OLE.

Optional PK Sub-study: **PPD**

Anti-GS-5745 Antibodies (ADA): Blood draws for ADAs will be done prior to dosing on Day 1, Weeks 4 and 8; and anytime at Week 12, and the 30-day follow-up visit of the blinded period. Blood draws for ADAs will be done prior to dosing at Week 24, and anytime at Week 64, the 30-day follow-up visit of the OLE.

Biomarker Blood Draws: Blood for biomarkers will be collected during the blinded period at Day 1 and, Weeks 4 and 12. For During the OLE, samples will be collected every 3 months, starting at Week 24.

TB testing:

A repeat QuantiFERON® TB-Gold In-Tube test will be performed annually (Week 54) for subjects continuing in the study. A repeat chest x-ray may also be performed annually, depending upon local TB screening guidelines.

Genomic Testing

Optional Genomic Testing: **PPD**

Test Product, Dose, and Mode of Administration:

Group 1:

GS-5745 300 mg (2 x 1 mL GS-5745 [150 mg/ml] SC injections) administered weekly

Group 2:

GS-5745 150 mg (1 x 1 mL GS-5745 [150 mg/ml] + Placebo-to-match 1 x 1 mL SC injections) administered weekly

Reference Therapy, Dose, and Mode of Administration:

Group 3:

Placebo-to-match (2 x 1 ml SC injections) administered weekly

Criteria for Evaluation:

Safety: Safety will be assessed during the study through the reporting of AEs, and by clinical laboratory tests, physical examinations, and vital sign assessments at various time points during the study.

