3.4. Duration of Treatment

Subjects will receive 12 SC injections of weekly study drug (GS-5745 or placebo) in the blinded period and up to 53 weekly doses of GS-5745 in the OLE.

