5.3. Dosage and Administration of GS-5745 and Placebo to Match

Subcutaneous injections of study drug (GS-5745/PTM) should be administered to 1 of 4 locations: to the right thigh, left thigh, right abdomen, or left abdomen (abdominal injections should be made at or below the level of the navel, avoiding the area within 5 cm [two inches] of the navel). If a subject is dosing their TNF inhibitor medication on the same day as their study drug, the subject should be instructed to inject their TNF inhibitor in a different site than the study drug. Information regarding which site was used for study drug injection will be collected throughout the study.

GS-5745 or placebo will be administered SC at the research center at Day 1 and Weeks 1, 4 and 8 during the blinded part of the study. All injections should be delivered within 1 hour of the first SC injection. The investigator or a qualified designee must be present during the administration of SC injections at Day 1 and Week 1. After training for SC injection at the study site, the subject will be allowed to administer the remaining weekly SC study drug doses at

home, except for those doses which coincide with scheduled study visits; in those cases, the study drug should be administered at the site, under direction of study staff (to enable timing for PK blood draws or other study procedures).

During the OLE portion of the study, GS-5745 will be administered SC at the research center at Weeks 12 and 13. Afterwards, subject will administer the subsequent weekly SC study drug doses at home, except for those doses which coincide with scheduled study visits; in those cases, the study drug should be administered at the site, under direction of study staff (to enable timing for PK blood draws or other study procedures).

In any part of the study, if the subject has a body temperature of $> 38^{\circ}\text{C}$ (100.4°F), or the subject feels unwell or is otherwise unfit to receive study drug at a given scheduled weekly injection, the subject should not be administered study drug. In consultation with the medical monitor, the Investigator may delay dosing until the parameters above have resolved.

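### The open-label dispensing footnote supplies no drug for the weekly home doses of Weeks 14 to 18

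*Protocol*

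**What the plan says.** The regimen is weekly throughout the extension. The Protocol Synopsis states: "In the OLE, study drug administration will occur weekly from Week 12 to Week 64". Section 3.4 allows "up to 53 weekly doses of GS-5745 in the OLE". Footnote h of the OLE schedule in Appendix 2 opens with "Patients receive SC injections once a week". Section 5.3 places the Week 12 and Week 13 doses at the research center and continues: "Afterwards, subject will administer the subsequent weekly SC study drug doses at home", apart from doses that fall on a visit day.

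The visit list in the Synopsis is: "Additional OLE study visits will occur at Weeks 13, 19, 24, 30, 36, 42, 48, 54, 60, and 64". There is no visit between Weeks 13 and 19.

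Supply is set by footnote g of the same OLE schedule. The normal quantity is six doses, dispensed "at these visits except for Week 12, 13 and week 64 when 1 dose will be dispensed". The footnote adds: "Site personnel will administer study drug at office visits when drug is dispensed".

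**The concern.** Footnote g gives Week 13 the same one-dose quantity as Week 12. That suits Week 12, because the next visit is a week later. It does not suit Week 13, because the next visit is six weeks later. A site cannot follow footnote g and also have the subject inject weekly at home under Section 5.3 and footnote h.

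If the footnote is followed, treatment stops for several weeks just after open-label 300 mg begins. Little else in the plan would catch this:

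- The missed-dose instructions for study drug in Protocol Section 5.3 are written for the blinded part and the first 12 doses.
- SAP Section 4.2.1 measures exposure from first to last dose and ignores interruptions.
- SAP Section 4.2.2 drops the adherence summary, so the gap would show only in the by-subject administration listing.
- The pre-dose PK and antibody samples planned for Week 24 would follow only the five doses of Weeks 19 to 23 since the gap.

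**Working it through.** **Inputs.** One dose per week from Week 12 to Week 64 (Synopsis; Section 3.4). Visits at Weeks 12, 13, 19, 24, 30, 36, 42, 48, 54, 60 and 64 (Synopsis; Appendix 2). Quantities from footnote g: 1 at Week 12, 1 at Week 13, 6 at each of the eight visits from Week 19 to Week 60, and 1 at Week 64. Visit windows of ±3 days at Week 13 and ±5 days at Week 19 (Appendix 2).

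**The plan's own figure.** Doses from Week 12 to Week 64 inclusive: 64 − 12 + 1 = 53. This reproduces Section 3.4.

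**Weeks 12 to 18.**
- Needed: 18 − 12 + 1 = 7.
- Supplied: 1 + 1 = 2, both used on site.
- Missing: 7 − 2 = 5, namely Weeks 14, 15, 16, 17 and 18.
- Interval from the Week 13 dose to the Week 19 dose: 6 × 7 = 42 days, against 7 planned.

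**Visit windows.** The shortest interval is 42 − (3 + 5) = 34 days and the longest is 42 + (3 + 5) = 50 days. Weekly doses falling strictly between the two visits number 4 (days 7 to 28) at the shortest and 7 (days 7 to 49) at the longest. The windows do not close the gap.

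**Leftover blinded stock.** The blinded-period footnote reads: "Study drug for 4 weekly doses will be dispensed at Weeks 1, 4 and 8". That is 3 × 4 = 12 doses, and Weeks 1 to 11 use 11. With full adherence one is spare. It is blinded supply, possibly placebo, so it cannot stand in for open-label 300 mg.

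**Whole extension.** Footnote g dispenses 1 + 1 + 8 × 6 + 1 = 51 doses. Against 53 this looks like a shortfall of 2, but the surplus comes after the gap: 6 − 5 = 1 spare from Weeks 19 to 23 and 6 − 4 = 2 spare from Weeks 60 to 63. Doses that can be given on schedule are 51 − 3 = 48, which is 53 − 5.

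**After the change.** With six doses at Week 13, one is given on site and five cover Weeks 14 to 18. Total dispensed is 1 + 6 + 48 + 1 = 56, and no week from 12 to 64 is without drug. Six doses at Week 12 and one at Week 13 also leaves no week from 12 to 18 uncovered, since 6 + 1 = 7.

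**If no Week 64 dose is intended.** Weeks 12 to 63 need 52 doses. As written 52 − 5 = 47 can be given, and all 52 after the change. The five-dose gap is the same either way.

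**The case against.** The strongest reply is that nobody would be misled. Weekly dosing is stated repeatedly, including in the footnote directly below the faulty one. Staff who have just given the Week 13 dose and are about to send a subject home for six weeks would probably ask about supply. The study procedures manual, cited in Protocol Section 6 and not available here, may give quantities. All of this lowers the practical risk. None of it corrects the footnote, and a manual that said six doses would contradict the protocol rather than amend it.

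It is also fair to say that the efficacy endpoints listed as primary and secondary are at Week 12, and that Section 6.4 requires the Week 12 procedures to be finished before OLE dosing starts. That stands, and it limits the point to OLE exposure.

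Three stronger readings are tempting but not supported:

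- **Footnote g is right about Week 64 and the table is wrong.** The dispensing row says no at Week 64 where footnote g says one dose. Section 3.4 and the Synopsis dosing paragraph fit a Week 64 dose. The 52-week duration in the Synopsis, Protocol Sections 3.2 and 3.3.1 and SAP Section 1.2 can be read as ending at Week 63. The documents do not settle which is meant.
- **The gap starts at Week 13, because that cell of the dispensing row is blank.** The blank may come from reading the table out of the PDF, and footnote g does give Week 13 a dose.
- **Subjects actually missed these doses.** Nothing in the documents shows this.

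**Conclusion.** The inconsistency is real and is wrong as written: seven doses needed for Weeks 12 to 18, two supplied, five missing on nominal dates (four to seven at the window limits). It assumes that footnote g is applied literally, that visit-day doses are given on site as the same footnote says, and that no document outside this set overrides it. It does not depend on the blank Week 13 cell or on how the Week 64 question is answered.

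Severity is minor to moderate. The consequence is an interruption in an optional extension, at a site that does not query the conflict. According to the SAP, the study was terminated on 5 June 2017 after 15 subjects had been enrolled, which further limits how many could have met the problem.

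**What to change.** Remove Week 13 from the one-dose exception in footnote g, so that six doses are dispensed there, and mark Week 13 in the Study Drug Dispensing row. Dispensing six at Week 12 and one at Week 13 would also work. Week 13 is a preference, because it keeps the home supply back until the second supervised injection. Carry the new quantity into whatever system or manual sets OLE dispensing. The protocol does not say which that is, since Section 5.1 describes the IXRS only for blinded supply up to Week 12.

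Separately, ask the sponsor to confirm whether a Week 64 dose is intended, and then bring footnote g, the dispensing row, the 53-dose figure and the 52-week duration into line.

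The text change is one week number and one table cell. Because Appendix 2 is protocol text, Sections 9.1.2 and 9.2.1 require IRB or IEC submission and approval before it takes effect, with about 40 centers planned. It is best bundled with another amendment.
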